7.2.1 Net Clinical Benefit: an important criterion for decision making

It should be noted that evidence of a significant difference in major morbidity is not necessarily an indication for early stopping of the trial since this might be balanced by a reduction in deaths or severe disability. For example one arm of the study may be associated with an increase in morbidity which is statistically significant, but may also be consistent with a reduction in deaths which is not statistically significant, and with net benefit (not statistically significant) for the other arm. Similarly, evidence of a significant increase in an intermediate measure of adverse outcome, such as intraventricular haemorrhage (IVH) or necrotising enterocolitis (NEC), in one arm of the study is not necessarily an indication to stop early, since this might be balanced by an overall reduction in deaths and/ or severe disability in the other arm of the study on follow up. Furthermore, major outcomes on follow up will not be determined until two years after trial entry. In both examples, it may be appropriate to continue the trial and indeed other related trials, until a clearer picture on net clinical benefit was obtained.

8 STATISTICS

8.1 Sample Size

Controls (early clamping) are expected to have a 30% rate of the primary combined outcome of mortality (10%) and major morbidity (20%) at 36 weeks post menstrual age. A sample size of 1600 would have 90% power to detect a reduction in absolute risk of 8% (27% relative risk reduction) in the primary outcome, allowing for 10% non-compliance at 2p = 0.05. If the non-compliance rate was 20%, this sample size would have more than 80% power to detect a reduction in absolute risk of 8%. About 534 babies are expected to be less than 27 weeks gestation.

The planned sample size of 1600 has 80% power at 2p=0.05 to detect an absolute risk reduction in mortality at 36 weeks post menstrual age of 4.2% from 10% to 5.8% and an absolute risk reduction of 8% (25% - 17%) in the outcome of mortality or severe disability to 24 months corrected gestation, assuming 10% non compliance. It gives 80% power to detect a reduction in absolute risk of major morbidity of 5.9% from 20% to 14.1%, assuming 10% non compliance. The expected sample of 534 babies < 27 weeks gestation gives 80% power to detect an absolute risk reduction of 13.4% from 60% to 46.6% in mortality and major morbidity, assuming 10% non compliance. The expected sample of 1066 babies of 27 ° weeks gestation or more gives 80% power to detect an absolute risk reduction absolute risk reduction of 6.1% from 15% to 8.9% in mortality and major morbidity, assuming 10% non compliance.

8.2 Statistical Analysis

The primary analyses will be performed on assigned treatment (intention to treat). Continuous data will be summarised using means for normally distributed variables and medians otherwise. Binary outcomes will be summarised using percentages. Groups will be compared using chi-square tests or t-test where appropriate. Adjusted analyses will use logistic or linear regression where appropriate. Time to event outcomes will be analysed with proportional hazards regression. Safety outcomes may be analysed using a treatment received analysis. No adjustments will be made for multiple comparisons.

Page 13 of 81

8.3 Prospective meta-analysis

Meta-analysis of multiple randomised controlled trials increases the overall sample size and power to demonstrate treatment effects. However, if meta-analysis is performed when results of trials are known, data dependent selection bias can occur. Trials with certain results can be deliberately included or excluded to manipulate the conclusions. A prospective meta-analysis (PMA) is a meta-analysis where randomised controlled trials are identified, evaluated and determined to be eligible before the results of any of them become known. PMA can therefore help to overcome some of the problems of retrospective meta-analyses. It enables: hypotheses to be specified a priori ignorant of the results of individual trials; prospective application of selection criteria; and a priori statements of intended analyses, including sub-group analyses, to be made before the results of individual trials are known. This avoids potentially biased, data dependent emphasis on particular subgroups. In addition, pooling of individual patient data allows more informative subgroup analyses to be conducted. The Australian Placental Transfusion Study will contribute to a proposed PMA of similar RCTs.

9 ADMINISTRATIVE ASPECTS

9.1 Ethics and regulatory compliance

This study will be conducted according to the Note for Guidance on Good Clinical Practice (CPMP/ICH/135/95) and in compliance with applicable laws and regulations. The study will be performed in accordance with the NHMRC Statement on Ethical Conduct in Research Involving Humans (© Commonwealth of Australia 2007) and the principles laid down by the World Medical Assembly in the Declaration of Helsinki 2008. The investigator shall comply with the protocol, except when a protocol deviation is required to eliminate immediate hazard to a mother or baby. In this circumstance the CTC, principal investigator and HREC will be advised. The trial will be registered with the Australian Clinical Trial Registry.

9.2 Study conduct

All study sites taking part in the trial will be required to participate in a start-up meeting on-site, to present the protocol and undergo training on study procedures and data collection methods. The Principal Investigator at each study site must apply for Human Research Ethics Committee (HREC) approval, submit all amendments and changes to the protocol and provide any necessary documentation for their site before they can enrol babies into the study.

9.3 Confidentiality

The study will be conducted in accordance with applicable Privacy Acts and Regulations. All data generated in this study will remain confidential. All information will be stored securely at the NHMRC Clinical Trials Centre, University of Sydney and will only be available to staff directly involved with the study.

9.4 Protocol amendments

Changes and amendments to the protocol can only be made by the Trial Management Committee. Approval of amendments by the Institutional HREC is required prior to their implementation. In some instances, an amendment may require a change to a consent form. The Investigator must receive approval/advice of the revised consent form prior to implementation of the change. In addition, changes to the Case Report Forms, if required, will be incorporated in the amendment.

The investigator should not implement any changes to, or deviations from, the protocol except where necessary to eliminate immediate hazard(s) to mothers or babies in the trial.

Page 14 of 81

9.5 Data Handling and Record Keeping

Trial data will be recorded on the CRFs provided. All required data entry fields will be completed. Data corrections will be done according to the instructions provided. The investigator will be asked to confirm the accuracy of completed CRFs by signing key CRFs as indicated.

Source documents pertaining to the trial must be maintained by investigational sites. Source documents may include a mother or baby's medical records, hospital charts, clinic charts, the investigator's participant study files, as well as the results of diagnostic tests such as X-rays, laboratory tests, and electrocardiograms. The investigator's copy of the case report forms serves as part of the investigator's record of a baby's study-related data.

The following information should be entered into the baby's medical record:

- a. Baby's name, contact information and protocol identification.
- b. The date that the baby entered the study, and study number.
- c. A statement that informed consent was obtained (including the date).
- d. Relevant medical history
- e. Results of key trial parameters.
- f. Occurrence and status of any unexpected serious adverse events.

g. The date the baby exited the study, and a notation as to whether the baby completed the study or reason for discontinuation.

All study-related documentation will be maintained for 23 years following completion of the study.

9.6 Study Monitoring

Data from this study will be monitored by Clinical Trials Program staff from the NHMRC Clinical Trials Centre (CTC). Monitoring will include centralized review of CRFs and other study documents for protocol compliance, data accuracy and completeness. Monitoring may include monitoring visits to investigational sites for source data verification, review of the investigator's site file and drug handling records. The CTC will be given direct access to source documents, CRFs and other study-related documents. By signing the informed consent form, the parents give authorized CTC staff direct access to the mother and baby's medical records and the study data.

9.7 Audit and Inspection

This study may be subject to audit or inspection by representatives of the CTC or representatives of regulatory bodies.

9.8 Clinical Study Report

Data will be entered and statistical analysis will be conducted by the NHMRC CTC. A Clinical Study Report will be issued which may form the basis of a manuscript(s) intended for publication.

9.9 Publication Policy

The Trial Management Committee will appoint a Writing Committee to draft manuscripts based on the trial data. Manuscripts will be submitted to peer-reviewed journal(s). The initial publication will be the report of the full trial results based on the main protocol using the study group name, with subsequent publications of data subsets. The Writing Committee will develop a publication plan, including authorship, target journals and expected dates of publication.

Page 15 of 81

7.9 Clinical Study Report	
7.10 Publication Policy	
8 LIST OF SUB-STUDY APPENDICES	
Appendix 1	
9 REFERENCES	33

SYNOPSIS

Primary clinical hypothesis:

An autologous transfusion of placental blood at birth will improve health outcomes in preterm babies. Placental transfusion by deferred cord clamping is associated with an 8% absolute risk difference, from 30% to 22% in mortality and/or major morbidity, at 36 weeks post menstrual age.

Study objective:

To establish if placental transfusion in preterm babies less than 30 weeks gestation will improve health outcomes compared with the standard practice of early cord clamping.

Study design:

This is a multicentre 2-arm parallel open label randomised controlled trial

Study interventions:

The two arms of the trial comprise:

(a) early cord clamping (which is the control arm)

(b) deferred cord clamping (for 60 seconds or more with the baby held below or at the level of the placenta)

Duration: 48 months for recruitment with a further 24 months for follow-up i.e. total study duration of 72 months.

Study population: babies of 29 ⁶ weeks gestation or less

Primary outcome

Death and/or major morbidity at 36 completed weeks post menstrual age

Secondary outcomes include

Incidence of the following outcomes up to 36 completed weeks post menstrual age unless specified otherwise:

- 1. Death
- 2. Major morbidity
- 3. Death and major morbidity in infants of 27 ° to 29° weeks gestation
- 4. Death and major morbidity in infants of 26 ⁶ weeks gestation or less
- 5. Death or major disability up to 3 years corrected age

Tertiary (hypothesis generating) outcomes include

Birth weight, number of exchange transfusions, number of partial exchange transfusions

Pre-defined subgroups:

- i. Gender
- ii. Age: Infants of 26 ⁶ weeks gestation or less or 27 ⁰ weeks gestation or more
- iii. Caesarean Section vs Vaginal birth

Power and Sample Size

At least 1500 infants and a primary outcome rate in the immediate clamping group of 41.6% will have 80% power to detect a 24% RRR, allowing for 30% non-compliance at 2p = 0.05.

Page 20 of 81

Determine whether deferring cord clamping for 60 seconds or more results in a decrease in mortality and major morbidity at 36 weeks post menstrual age for pre term babies born less than 30 weeks gestation.

[figure not shown]

Figure 1. Australian Placental Transfusion Study schema.

Page 21 of 81

1 BACKGROUND INFORMATION

Babies born less than 30 weeks of gestation have increased incidence of mortality, brain damage and other morbidities.¹ Death and disability often results from inflammatory damage mediated by hypoxia, hyperoxia, cardiovascular compromise, ischaemia, reperfusion injury, infection or a combination of these factors. Placental transfusion is a low cost, simple haemodynamic intervention that may reduce these morbidities and mortality in very preterm babies.

Summary of the clinical scenario

Placental transfusion at birth is achieved by deferring clamping of the umbilical cord or by the less frequently reported method of 'milking' residual cord blood into the baby after clamping. Table 1 summarises an unpublished updated meta-analysis of 11 RCTs of placental transfusion in 494 babies (Reynolds unpublished data). The majority of these data are derived from studies undertaking delayed cord clamping with only one study involving the 'milking' strategy.

Table 1: Effects of placental transfusion versus early clamping in 11 RCTs, 494 babies < 37	weeks gestation

Outcome		No. of babies	Effect type	Estimate (95% confidence interval)
Potential benefits				
Haematocrit* 1 hr after birth	6	281	WMD ^T	3.00 [1.49, 4.51]
Haematocrit* 4 hr after birth	4	134	WMD	5.40 [3.52, 7.28]
Number of blood transfusions	5	212	WMD	-1.32 [-1.93, -0.70]
• Transfused for low blood pressure	2	58	RR ^	0.38 [0.18, 0.84]
Intraventricular haemorrhage (IVH)	10	436	RR	0.54 [0.37, 0.78]
Necrotising enterocolitis (NEC)	6	281	RR	0.61 [0.43, 0.88]
Late onset sepsis (LOS)	1	72	RR	0.1 [0.01, 0.85]
Mortality	11	480	RR	0.84 [0.43, 1.63]
• Temperature on admission (°C) [#]	3	143	WMD	0.14 [-0.03, 0.31]
Potential adverse effects				
Peak serum bilirubin (micromol/L)	7	320	WMD	11.13 [1.75, 20.51]

* packed cell volume; ^T WMD weighted mean difference; ^A Relative risk; [#] Rabe et al., 2008²

The evidence suggests that placental transfusion in babies <37 weeks gestation is safe, well tolerated and reduces the risks of intraventricular haemorrhage, necrotising enterocolitis and late onset sepsis by 40% or more. However, power was inadequate to exclude a moderate difference in mortality. Furthermore the results, especially for sepsis, are based on small numbers and must be viewed with caution. IVH reported above is for all grades of IVH and there is very little data on severe IVH. We were also unable to exclude from the analyses babies of 31-36 weeks gestation, who outnumber very preterm babies by more than 10:1 and who are at much less risk of adverse outcome. Nevertheless, the reductions in intraventricular haemorrhage, necrotising enterocolitis and late onset sepsis are important, and each is associated with mortality or later disability. If even a moderate decrease in these morbidities were confirmed in babies <30 weeks gestation, placental transfusion would have major implications for their survival and healthy development.

The main determinants of placental transfusion are time of cord clamping, uterine contraction and the position of the baby. Placental transfusion increases the blood volume by 35-60% in term babies if cord clamping is delayed for three minutes. If the infant is kept at or below the level of the placenta, about 25-30% of this transfusion occurs in the first 10-15 seconds. Umbilical arterial constriction is present by 45 seconds. Placental transfusion is completed by 1 minute if ergometrine is given early

[figure not shown]
Page 22 of 81

in the third stage of labour, and by 30 seconds if the baby is lowered to 40 cm below the introitus, illustrating the importance of hydrostatic pressure.^{3,4} Saigal *et al.* found that a complete placental transfusion produced a 47% and 50% increase in blood volume in preterm and term babies, respectively. Over half the full transfusion occurred by 1 minute in the preterm babies. Babies held 15 cm above the introitus for 1 minute received 60% of the transfusion received by babies held below it.⁵

The increase in blood volume provided by placental transfusion may be physiologically appropriate, and necessary, because the central haemodynamic event at birth is the rapid opening up of new vascular beds in the lungs.⁴ Looked at another way, early clamping may deprive the baby of a substantial volume of blood. This causes volume depletion and systemic and peripheral hypoperfusion as pulmonary vascular beds must be filled with blood from the systemic circulation instead. This is well compensated for in normally delivered term babies, but may not be after Caesarean section (when the uterus is often not contracting) or in preterm babies. The preterm fetus responds to volume expansion by intrauterine blood transfusion with a rapid increase in plasma concentrations of natriuretic peptide.⁶ Transudation or diuresis after placental transfusion could help explain why the mean haematocrit rises 1 and 4 hours after birth [Table 1].

Lung aeration and cardio-respiratory adaptation

Clamping the cord increases systemic vascular resistance by excluding the low resistance placenta from the neonatal circulation. Cord clamping also abolishes placental venous return to the ventricles and halves ventricular filling. ⁷ Both these effects substantially decrease output from the right ventricle. However, cord clamping does not necessarily decrease left ventricular output if the lung is aerated, because this reduces pulmonary vascular resistance, causing the shunt across the ductus arteriosus to reverse (left-to-right). This left to right shunting increases pulmonary blood flow (Figure), helping maintain venous return from the lungs and left ventricular output. ⁷

Pulmonary blood flow, cord clamping and ventilation

Clamping the cord without first aerating the lungs leads to persistently high pulmonary vascular resistance, which prevents reversal of blood flow and left to right shunting through the ductus arteriosus. As a result, pulmonary venous return, left ventricular output and cerebral blood flow may all initially be low, but then rapidly increase with lung aeration.

Aeration of the lungs before clamping the cord, either through spontaneous breathing or by positive pressure support, may stabilize cerebral blood flow in a smoother transition to the postnatal circulatory state. In apnoeic infants, lung aeration can be achieved with the cord intact before cord clamping by applying mask IPPV, using air or oxygen.

Page 23 of 81

Haematocrit correlates closely with red cell volume,⁸ which is inversely associated with risk of respiratory distress syndrome.⁹ In RCTs, placental transfusion increased initial haematocrit, blood pressure and oxygenation, and reduced use of surfactant and duration of ventilation or added oxygen.^{10,11,12} De Halleux *et al.* reported that decreased oxygen affinity after transfusion with adult blood increases the oxygen available to the tissues of pre-term babies.¹² This may increase oxygen toxicity to brain, eye¹⁴ and lung. By reducing exposure to adult donor blood transfusions, [Table 1] placental transfusion may reduce this oxygen toxicity. Placental transfusion may also increase total transfer of immunoglobulin to the infant. Lastly, preterm cord blood is rich in haemopoietic precursor and stem cells. As well as enhancing bone marrow function and immunocompetence against infection, these may have anti-inflammatory, neurotrophic and neuro-protective effects.¹⁵

Although our meta analysis [Table 1] showed no statistically significant negative impact on safety from placental transfusion in babies < 37 weeks gestation overall,^{2, 16} some preterm babies < 30 or <27 weeks gestation may be at higher risk of hypothermia, low Apgar scores, IVH, NEC or death if resuscitation is delayed until the cord is clamped after 60 seconds or more, especially the most immature or compromised, in whom myocardial dysfunction on echocardiography is common. Placental transfusion may increase serum bilirubin (a breakdown product of haemoglobin) and volume expansion with placental blood may be poorly tolerated in shock, asphyxia, or placental vascular disease.^{17, 18, 19} On the other hand, continuing perfusion with warm, oxygenated placental blood is well tolerated during the EXIT procedure, in which fetuses with complex airway problems are partially delivered by Caesarean section and supported by the placental circulation for 20 minutes or more while the airway is stabilized. Continuing placental transfusion might improve hypothermia, hypoglycaemia, gas exchange, hypovolaemia and shock.

Results from the APTS pilot study comparing (i) delayed cord clamping, (ii) cord milking and (iii) both delayed cord clamping and milking combined with (iv) immediate cord clamping (unpublished) indicated that compliance with the 4 intervention arms was acceptable. There was no difference in haemoglobin at 6 hours after birth between the 4 treatment arms in the first 40 babies studied and no safety issues with any of the arms. It was thus recommended by the TMC to commence the main study comparing immediate cord clamping with deferred cord clamping, for which there is most data currently available.

This two arm study is proposed to establish if placental transfusion in preterm babies less than 30 weeks gestation will improve health outcomes compared with the standard practice of early cord clamping.

2 TRIAL OBJECTIVES

To establish if placental transfusion, using deferred cord clamping for 60 seconds or more while holding the baby at or below the level of the placenta, will improve health outcomes compared with standard early cord clamping in pre term babies less than 30 weeks of gestation.

3 TRIAL DESIGN

3.1 Design

This is a multi centre, two arm parallel, open label randomised controlled clinical trial

3.2 Consent

All mothers considered by the obstetric team to have a reasonable chance of delivering before 30 weeks gestation are eligible. Consent will be sought by members of the delivery team or appropriate research staff at any time during pregnancy. For example, if it is anticipated some weeks in advance that delivery will be necessary before 30 weeks gestation, consent may be obtained well in advance of randomisation.

3.3 Randomisation

Timing of randomisation

While consent can be attained at any time, randomisation should only take place when delivery is considered inevitable, for example when labour is considered irreversible or when the operating theatre is booked for Caesarean Section and the baby's estimated gestation is less than 30 weeks gestation. Randomisation should be performed allowing sufficient time to use the Interactive Voice Response System i.e. at least ten minutes before the expected birth, or longer than this for multiple births.

Method of randomisation

Randomisation can be done by any member of the obstetric, midwifery, or neonatal team using a phone to call a computerised interactive voice response system.

Randomisation will be performed by using an interactive voice response system built by an independent statistician at the NHMRC Clinical Trials Centre, University of Sydney. All data will be stored securely by the statistical group at the centre.

Randomisation will be by the method of minimisation with two strata: Institution and Gestational age (<27 weeks; >=27 weeks). Multiple births will be randomised separately.

3.4 Endpoints

3.4.1 Primary outcome

Death and/or major morbidity at 36 completed weeks post menstrual age.

Morbidity is defined by one or more of the following obtained from the medical record:

- Brain injury on ultrasound
- Severe retinopathy
- Necrotising enterocolitis
- Late onset sepsis

Page 25 of 81

3.4.2 Definitions of primary outcome for study

Morbidity Measures

Based on definitions used by the Australian and New Zealand Neonatal Network.²⁰

Brain injury on ultrasound

Grade of 3 and 4 IVH (major intraventricular haemorrhage) seen on ultrasound according to the system of grading defined below:

- 1. Subependymal germinal matrix bleed
- 2. IVH without ventricular distension
- 3. IVH with ventricular distension with blood
- 4. Intraparenchymal haemorrhage

Or echodense intraparenchymal lesions, periventricular leukomalacia, porencephalic cysts or ventriculomegaly (97 percentile plus 4mm), or

- Severe retinopathy warranting treatment with laser surgery, cryotherapy or monoclonal antibody therapy or Stage 4 retinopathy (irrespective of whether treatment was warranted), or
- Necrotising enterocolitis diagnosis of proven Necrotising Enterocolitis with the following signs:
 - 1. at least one systemic sign: temperature instability, apnoea, bradycardia or lethargy and at least one intestinal sign: residual of 25% of the previous feed on 2 consecutive occasions, or abdominal distension, or vomiting or faecal blood
 - profile consistent with definite NEC including at least one of the following: abdominal wall cellulitis and palpable abdominal mass, or pneumatosis intestinalis, or portal vein gas, or a persistent dilated loop on serial X rays, or a surgical or post mortem diagnosis.
 - 3. warranted treatment for NEC, which included nil by mouth and antibiotics

Late onset Sepsis

Systemic sepsis is defined as a clinical picture consistent with sepsis, and either a positive bacterial or fungal culture of blood and/or cerebrospinal fluid, or a positive urine culture by sterile collection only, and at least 5 days of antibiotic treatment. At least one episode of systemic sepsis with date of culture from at least 48 hours after birth.

General guidelines for identifying positive cultures include:

Isolation of organisms from one blood culture and, after considering clinical/laboratory evidence, decision made to give antibiotics with therapeutic intent against this organism. Infections with coagulase – negative staphylococci, and other potential contaminants, or group β streptococcal antigen detected in urine should be included only if the baby is considered clinically septic and there is supporting evidence such as raised white cell count or thrombocytopenia. Viral infections must be proven by culture and/ or haematological results consistent with infection. The following must not apply: mixed CNS or other skin flora contaminant; same blood organisms isolated from blood during the previous 14 days – repeat isolate.

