3.4.3 Secondary outcomes

Incidence of the following outcomes up to 36 completed weeks post menstrual age unless specified otherwise:

- 1. Death
- 2. Death or brain injury
- 3. Major morbidity (see above for components of combined morbidity)
- 4. Death or major disability up to 3 years corrected age
- 5. Death up to 3 years corrected age
- 6. Major disability up to 3 years corrected age
- 7. Brain injury on ultrasound
- 8. IVH
 - I. IVH all grades

Page 26 of 81

- II. grades 3 and 4
- III. grade 4
- 9. Severe retinopathy defined as treatment for ROP or stage 4 ROP
- 10. Necrotizing enterocolitis
- 11. Late onset sepsis
- 12. Patent Ductus Arteriosis requiring treatment
- 13. Chronic lung disease (also known as bronchopulmonary dysplasia) defined as receiving supplemental oxygen or any form of assisted ventilation at 36 completed weeks post menstrual age for 4 consecutive hours in a 24 hour period

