- Chronic lung disease (CLD) removed from primary outcome definition as per IDSMC letter of recommendation. Long term respiratory support is now routine care and not a marker of CLD. CLD remains a secondary outcome. (Section 3.4.2)
- Addition of predefined subgroup: Caesarean section vs. vaginal birth. (Sections 3.4.6)
- Additional example of contraindication to placental transfusion (monochorionic twin pregnancies in which there is confirmed twin-twin transfusion) provided in exclusion criteria, in response to site queries. (Section 4.3)
- Sample size information updated to reflect observed compliance rates. Clarification of ITT population to exclude stillborn babies and babies born >30 weeks (Sections 8.1 and 8.2)
- Clarification that only suspected unexpected and related adverse events require expedited reporting, as unexpected SAEs are common in the preterm population. (Section 6.2)
- Clarification regarding Net Clinical Benefit and early stopping rules. (Section 7.2.1)
- Addition of interim analysis after the first 500 patients and then annually thereafter. Updates to reflect IDSMC request and current practice. (Section 7.2)
- Clarification of primary outcome definitions, including:
 - Severe retinopathy definition updated to include Stage 4 retinopathy regardless of whether it was treated. Stage 4 ROP is a severe condition, sufficient to meet the outcome definition regardless of treatment status. (Section 3.4.2)
 - Additional detail provided that "clinical picture consistent with sepsis" requires at least 5 days of antibiotic treatment to meet outcome. (Section 3.4.2)

- Clarification of secondary follow-up outcome, including up to 3 years' corrected age and use of "major disability" terminology. (Section 3.4.2)
- Addition of "Death or brain injury" as a secondary outcome. Brain injury or death due to brain injury is considered an important secondary outcome for this cohort. (Section 3.4.2)
- Administrative clarification of "36 weeks post menstrual age" to mean 36 completed weeks (throughout)
- No formal amendments to the APTS Trial Protocol were made after V4.0 (1 Jul 2016).

Changes to the APTS Primary Outcome in The APTS Childhood Follow Up Study:

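### The 5-day antibiotic requirement for late-onset sepsis has no exception for death, so an infant who dies on treatment sooner is scored as free of sepsis in two secondary outcomes

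*Supplement*

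**What the plan says.** Protocol V4.0, section 3.4.2, sets three conditions for systemic sepsis: a compatible clinical picture, a positive culture of blood, cerebrospinal fluid or sterile urine, and a minimum treatment length. The last part reads "or a positive urine culture by sterile collection only, and at least 5 days of antibiotic treatment". Timing is set separately: "At least one episode of systemic sepsis with date of culture from at least 48 hours after birth".

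The Summary of Changes from V3.0 to V4.0 explains the added condition. It says that the clinical picture of sepsis "requires at least 5 days of antibiotic treatment to meet outcome".

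Section 3.4.3 then lists two secondary outcomes, scored without death, that use this definition: "11. Late onset sepsis" and "3. Major morbidity (see above for components of combined morbidity". The primary outcome in section 3.4.1 combines the same morbidities with death.

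**The concern.** A minimum treatment length helps to screen out contaminated cultures and courses stopped because infection was ruled out. Death also ends a course early, for the opposite reason, and the rule does not separate the two. To be counted, an infant must survive long enough to complete 5 days of antibiotics.

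Other components in section 3.4.2 avoid this. Stage 4 retinopathy counts whether or not treatment was called for. Necrotising enterocolitis accepts a diagnosis made at surgery or autopsy for its disease-profile criterion and sets no minimum treatment length.

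At stake is the reading of two pre-specified secondary outcomes. If one arm has fewer early septic deaths because the infection was prevented, the sepsis outcome shows no gain from those cases. If it has fewer because infected infants survived, the sepsis outcome counts more cases in that arm. The Background section names late-onset sepsis among the morbidities behind the trial's rationale, so readers will look at this row.

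**Working it through.** The plan states no figure on this point, so there is none to reproduce. The check is of the wording, followed by an illustration of size.

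**1. Does the 5-day condition apply to all cultures or only to urine?** Taken alone, the sentence in 3.4.2 could tie the 5 days to the urine culture that precedes it. The Summary of Changes attaches the condition to the clinical picture of sepsis and says that this "requires at least 5 days of antibiotic treatment to meet outcome". It therefore applies to every culture type.

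**2. Is there an exception elsewhere?** The nearest text is in the guidelines on positive cultures in 3.4.2: "decision made to give antibiotics with therapeutic intent against this organism". That helps decide whether a culture counts as positive. It does not waive the treatment length. Nothing else in the documents shown makes an exception for death.

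**3. How infants are scored.** Each infant below has the clinical picture and a qualifying culture at 48 hours or later.

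| Course | Primary composite | Outcome 11, sepsis | Outcome 3, major morbidity |
|---|---|---|---|
| Completes 5 days of antibiotics, survives | event | event | event |
| Dies after 5 or more days of antibiotics | event | event | event |
| Dies on antibiotic day 2, earlier qualifying episode | event | event | event |
| Dies on antibiotic day 2, no earlier episode, but brain injury, severe retinopathy or NEC | event | **not counted** | event |
| Dies on antibiotic day 2, no earlier episode, no other component | event | **not counted** | **not counted** |

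**4. Size, under assumptions.** The documents give neither a sepsis rate nor a rate of early septic death. Take 750 infants per arm (half of the 1,500 in section 8.1), a true sepsis rate *s* of 15% to 35%, and a share *f* of 2% to 10% of septic infants who die before 5 days of antibiotics with no earlier episode.

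- Uncounted cases per arm = 750 × *s* × *f*. Lowest: 750 × 0.15 × 0.02 = 2.25. Highest: 750 × 0.35 × 0.10 = 26.25.
- Suppose sepsis is equally common in both arms, and deferred clamping cuts the early-death share by 30% by turning those cases into survived sepsis. The true relative risk is 1. The scored one is *s*(1 − 0.7*f*) / *s*(1 − *f*), and *s* cancels:
 - *f* = 2%: 0.986 / 0.980 = 1.006
 - *f* = 5%: 0.965 / 0.950 = 1.016
 - *f* = 10%: 0.930 / 0.900 = 1.033

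A more extreme case: qualifying sepsis is 20% in each arm, and early-fatal sepsis is 2% with immediate and 1% with deferred clamping. The true rates are 22% and 21% (relative risk 0.21 / 0.22 = 0.95), but they are scored as 20% and 20% (relative risk 1.00).

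**5. Against sampling error.** With 782 and 784 infants (follow-up SAP, Table 2) and 20% in each arm, the standard error of the difference is √[0.2 × 0.8 × (1/782 + 1/784)] = 0.020, or 2.0 percentage points. The 1-point shift in the extreme case is about half of that. The 95% interval around a relative risk of 1.00 would be about 0.82 to 1.22.

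**The case against.** The strongest reply is that the consequence is slight and largely visible elsewhere. The infant is an event in the primary composite, and death is itself secondary outcome 1. Table 10 of the follow-up SAP lists causes of death by arm, with rows for septicaemia and meningitis, so a fall in fatal sepsis would show there among follow-up infants. Protocol section 7.2.1 already warns the monitoring committee that more morbidity may be balanced by fewer deaths. Retinopathy needing treatment and chronic lung disease at 36 weeks also cannot be observed in infants who die early. Finally, the only SAP shown covers the 24-month follow-up. A 36-week analysis plan or the case report form might say how such infants are classified and which denominator is used.

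All of this limits the consequence, but none of it changes how outcomes 11 and 3 are scored under the governing definition. The comparison with retinopathy and lung disease is also imperfect: those infants die before the condition can be observed, whereas here the infection has already been shown by culture and is then discounted.

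A reader might infer from the clause that the most severe septic cases as a class disappear. They do not: an infant who dies of sepsis after 5 days of treatment is counted, and so is one with an earlier qualifying episode. A reader might also take the cut-off as day 5 of life. It is days of antibiotic treatment.

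**Conclusion.** The point stands as a narrow misclassification in two secondary outcomes. The wording is clear once the definition is read with the Summary of Changes: an infant with otherwise qualifying late-onset sepsis who dies before completing 5 days of antibiotics for that episode is not counted. The loss is conditional on no earlier qualifying episode for outcome 11, and also on no other component for outcome 3.

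The primary outcome and its power are untouched. The direction of the bias is predictable, against the arm with fewer early septic deaths. Its size cannot be found from the documents. Under the assumed ranges above it is probably small and well within sampling error, and smaller still for outcome 3, where other components will often capture the infant.

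A reader might go further and conclude that the trial would report a false harm on sepsis. The documents do not support that. It would need assumed rates near the top of the range and averted deaths becoming survived infections, and even then the shift is about 1 percentage point against a standard error of about 2.

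**What to change.** In section 3.4.2, after "or a positive urine culture by sterile collection only, and at least 5 days of antibiotic treatment", add: *or antibiotic treatment with therapeutic intent for that episode cut short by death before 5 days*. Keep the existing rules on contaminants and repeat isolates. Apply the amended definition to outcomes 11 and 3, and re-classify, blinded to allocation, the infants who died with a positive culture. If the definition is to stay as it is, report this version as a sensitivity analysis for the two outcomes.

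The cost is one clause and a blinded check of the records of infants who died with a positive culture. The price is a small loss of specificity: some terminal cultures, and some infants who died of another cause during treatment, may be admitted. Tying the clause to treatment of that episode, rather than to any death, keeps this small. The change concerns outcome classification only and does not touch clinical care.
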